10. CONFIDENTIALITY

In accordance with GCP and with the national data protection laws, all information concerning the subjects in the study must be treated as strictly confidential by all persons involved in the study.

The investigator acknowledges that any and all information acquired from the Sponsor or its designee or developed or acquired in connection with the study are strictly confidential. The investigator will not disclose any confidential information to any third party nor use confidential information for any purpose without first obtaining the consent of Sponsor in writing. Such consent shall be deemed to have been given for disclosure to any person for whom the investigator is responsible at his/her center, but only so far as required for the purposes of the study, and, in the case of disclosures to staff, only if such staff are bound by obligations of confidentiality no less strict than those set out herein.

11. PROTOCOL AMENDMENTS

The Sponsor will document modifications to the protocol in the form of a written amendment. Protocol modifications that impact subject safety or the validity of the study must be approved by the IRB before implementation. In the case of a medical emergency, to remove immediate apparent hazard to subjects, a change may be made preferably after discussion with the Sponsor or its designee. In these instances, the IRB and FDA will be notified as soon as possible.

12. DATA MANAGEMENT

Electronic data capture (EDC) will be utilized for this study. Study worksheets will be provided by the Sponsor or its designee to the site before data collection. In order to facilitate data entry, the worksheets coincide with the data entry pages in the EDC system. The design of the data entry screens will follow the same flow as the provided worksheets in order to insure minimal issues during data entry. If the site elects to use the worksheets, appropriate worksheets will be completed and initialed or signed where indicated at each examination. All worksheets will be completed in a legible manner in black/blue ink. Alternatively, the site may elect to use their own source documents. It is expected there will be source data for all entries in the EDC.

Any corrections to the worksheets will be made by drawing a single line through the incorrect entry, recording the correct information, and initialing and dating the change.

The study worksheets and data entered in the EDC system will be audited by the Study Monitor.

Once the data is ready to be entered into the EDC System, then the site will begin entering the data into the system. Afterwards, the monitor will review the data against the source documents and/or worksheets and either approve the data records or create queries to the site for further review. If the data records are deemed "clean" with the approval of the monitor, then the investigator can e-sign the records. Finally, when the data records are ready to be locked, the data manager will perform the interim lock in the system. However, the data manager also has the right to unlock the data record if any updates to the data are necessary.

Data are protected by preventing unauthorized users from accessing the system with the use of username and password combination. In addition, each individual user will be assigned a specific role in the EDC System which will grant that user the right to view, edit and/or delete the data. Furthermore, any changes to the data are captured in the EDC System's audit trail where a reason for change is required.

All clinical data generated in the study will be submitted to the Sponsor or designated CRO for quality assurance review and statistical analysis. All worksheets and data entered into the EDC system will be reviewed for completeness and evident recording errors will be rectified by contact with the appropriate clinical site. Computerized data checks will be used to identify unusual data entries for verification prior to statistical analysis.

To minimize the amount of missing data, investigators will be trained on the deleterious effect that missing data have on trial integrity and credibility and that missing data could diminish the scientific value of all subjects' altruistic contributions.

13. RECORD KEEPING AND RETENTION

Data generated for the study should be stored in a limited-access file area and be accessible only to representatives of the study site, the Sponsor and its representatives and FDA/relevant health authorities/regulatory agencies. All reports and communications relating to study subjects will identify subjects only by initials and subject identification number. Complete subject identification will be kept by the investigator. This information will be treated with strict adherence to professional standards of confidentiality.

An investigator must in reasonable time, upon request from any properly authorized officer or employee of FDA/relevant health authority or regulatory agency, permit such officer or employee to have access to requested records and reports, and copy and verify any records or reports made by the investigator. Upon notification of a visit by the FDA/relevant health authority or regulatory agency, the investigator will contact the Sponsor or its designee immediately. The investigator will also grant Sponsor representatives the same privileges offered to FDA/relevant health authority or regulatory agents/officers/employees.

The Investigator must provide the Sponsor or its designee with the following documents prior to study initiation and retain a copy in the study file:

- A completed and signed Form FDA 1572. If during the course of the study any changes occur that are not reflected on the 1572, a new 1572 form must be completed and returned to the Sponsor or its designee for submission to the FDA.
- Current signed curriculum vitae (within 2 years prior to study initiation) and current medical licenses for the Principal Investigator and all co-investigators listed on the 1572.
- A copy of the original approval for conducting the study by the IRB. Renewals, with continuance of the study, must be submitted at yearly intervals or as required by IRB policy.
- A copy of the IRB approved informed consent form.
- IRB member list and DHHS General Assurance Number (if IRB has an Assurance number).
- Signed Financial Disclosure Form for all personnel listed on the 1572 with a statement of non-voting by study staff.
- The signature page of this protocol signed and dated by the Principal Investigator.
- The signature page of the Investigator Brochure signed and dated by the Principal Investigator.

In addition to the documents listed above, the study site will also retain the following items:

- Certifications and laboratory reference ranges for all local laboratories used for this study.
- Copy of delegation of authority log.
- All original informed consent forms with required signatures.
- All IRB correspondence (i.e., informed consent [including any approved revisions], protocol, AE, advertisements, newsletters).
- Copy of the Study Monitoring Log
- Clinical and non-clinical supply shipment forms
- Copies of all pertinent correspondence pertaining to the study (except budget issues) between the Sponsor or the CRO and the site
- Copies of all SAEs reports submitted to the Sponsor or its designee
- Copies of all IND Safety Reports submitted to the site by the Sponsor or its designee
- Copies of approved package labeling

All study-related records must be maintained for at least 2 years after a marketing application (NDA/BLA) is approved for the drug; or if an application is not approved for the drug, until at least 2 years after shipment and delivery of the drug for investigational use is discontinued and FDA/health authorities or regulatory agencies have been notified. The Sponsor will notify the principal investigator when records are no longer needed. The investigator will not discard any records without notifying the Sponsor. If the principal investigator moves from the current investigational site, the Sponsor should be notified of

the name of the person who will assume responsibility for maintenance of the records at the investigational site or the new address at which the records will be stored. The investigator will notify the Sponsor as soon as possible in the event of accidental loss or destruction of any study documentation.

14. INVESTIGATOR FINAL REPORT

The investigator shall provide the IRB and the Sponsor with an accurate final report within 2 months after completion, termination or discontinuation of the study. The final report may not precede final data submission which has not been monitored.

15. STUDY REPORT AND PUBLICATION

The data resulting from this study will be the proprietary information of the Sponsor and may be made public after all data have been analyzed and the study results are available. None of the data resulting from this study will be allowed to be presented or published in any form, by the investigator or any other person, without the prior written approval of the Sponsor. At the end of the study, a clinical study report will be written by the Sponsor or its designee.

Appendix 1. Schedule of Evaluations

Helixmith Co., Ltd. Page 32 of 45 Protocol VMDN-003b/C CONFIDENTIAL

SCHEDULE OF EVALUATIONS AND VISITS

Procedure	Day 270 Up to 14 D prior to Day 365	12M Day 365 ± 14 D
Informed Consent	✓	
Safety and Efficacy Parameters		
Vital Signs		✓
Concomitant Medications		✓
Daily Pain and Sleep Interference Diary		✓
PGIC		√
Adverse Events		✓

Helixmith Co., Ltd. Page 33 of 45 Protocol VMDN-003b/C CONFIDENTIAL

Appendix 3. Daily Pain and Sleep Interference Diary – One Day Sample

Please complete one form (a + b + c) each day starting on the day indicated by the clinic around 8 pm every night. Question 1a: indicate the day of the week, the date and time. Return the completed forms to the clinic at your next visit. Please circle a number from 0 to 10 that best describes your status using a fine or medium point pen. Date: $_{\overline{DD}}$ / $_{\overline{MMM}}$ / $_{\overline{YYYY}}$ -Time: ____ am / pm (circle one) **1a. DAY** (Day of week) 1b. Please rate your average pain in your legs (below the knee, this includes pain in your foot) during the past 24 hours. 0 1 2 3 5 7 8 9 10 No Moderate Worst Pain Pain possible pain 1c. Please rate how much your pain in your legs (below the knee, this includes pain in your foot) interfered with sleep during the past night. 0 5 7 10 Did not Completely interfered with interfere with sleep sleep Patient's Initials: The study coordinator will check the diary for completeness. Any omissions or ambiguous

Protocol VMDN-003b/C CONFIDENTIAL Helixmith Co., Ltd.

answers will be clarified by the subject prior to leaving the clinic. Note, the subject will be

required to initial and date each page of the diary.

Appendix 4. Patient's Global Impression of Change

Patient Global Impression of Change (PGIC) Scale

Since the start of the study, my overall status is: Check (\checkmark) one box only: Very Much Improved $\prod 1$ □ 2 Much Improved Minimally Improved ☐ 3 □ 4 No Change Minimally Worse □ 5 □ 6 Much Worse □ 7 Very Much Worse Patient's Initials: Date: _____

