3.2. STUDY DESIGN

This is a prospective, observational, non-interventional study for long-term follow-up of subjects previously enrolled in the VMDN-003 study: a phase III, double-blind, randomized, placebo-controlled, multicenter, 9-month study designed to assess the safety and efficacy of VM202 in subjects with painful DPN. Subjects currently enrolled or having recently completed the VMDN-003 trial will be invited to provide informed consent and enroll in this extension study.

After providing consent, subjects will be asked to complete a 7-Day Daily Pain and Sleep Interference diary and one visit 365 ± 14 days after their VMDN-003 Day 0 visit. Diaries will be collected at the visit, along with vital signs, concomitant medications, adverse events, and the PGIC questionnaire.

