3.4.3. DAY 270 UP TO 14 DAYS PRIOR TO SCHEDULED DAY 365 VISIT

Informed consent

Study subjects may sign the informed consent form for the extension study after completing Day 270 assessments for study VMDN-003. Alternatively, subjects may return to the research center at any time following Day 270 but no later than 14 days prior to their scheduled Day 365 visit to sign the informed consent form.

$DAY 365 \pm 14 DAYS$

The only study visit will be scheduled 365 days \pm 14 days after the subject's VMDN-003 Day 0 visit.

The subject will be asked to completed the Daily Pain and Sleep Interference Diary within 14 days prior to the Day 365 visit

STUDY VISIT PROCEDURES

- Daily Pain and Sleep Interference Diary to be completed within 14 days prior to the visit
- Vital Signs
- Concomitant Medications
- **PGIC**
- Adverse event assessment

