4.4. PATIENT'S GLOBAL IMPRESSION OF CHANGE (PGIC)

The patient's global impression of change after treatment will be measured using the Patient's Global Impression of Change (PGIC) questionnaire. This questionnaire measures a patient's perception of how treatment has affected their level of activity, symptoms, emotions, and overall quality of life. Each descriptor is ranked on an intensity scale of 1 = Very Much Improved; 2 = Much Improved; 3 = Minimally Improved; 4 = No Change; 5 = Minimally Worse; 6 = Much Worse 7 = Very Much Worse. This test will be self-administered during study visits on Day 365.

Upon completion of the questionnaire, the study coordinator will check the questionnaire for completeness. Any omissions or ambiguous answers will be clarified by the subject prior to leaving the clinic. The PGIC can be found in Appendix 3. Note, the subject will be required to initial and date the PGIC.

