8.4. Patient's Global Impression of Change (PGIC)

Patient's Global Impression of Change (PGIC) results will be summarized at Day 365. The change will be assessed relative to the VMDN-003 baseline. The results will be summarized by the following three categories:

- Very Much Improved or Much Improved
- Minimally Improved/Worsened or No Change

Much Worse or Very Much Worse

PGIC will be analyzed by Cochran-Mantel-Haenszel (CMH) test to account for the stratification variable and row means scores differ statistic (row variable: treatment group, column variable: 3-category data of PGIC) will be used.

PGIC results will be listed.

Efficacy data will be summarized by treatment group and by treatment group within baseline gabapentin and pregabalin use.

9. Safety and Tolerability Analysis

Safety assessments will be collected at the Day 365 visit and include adverse events, concomitant medications, and vital signs.

All safety analyses will be performed on the safety population by actual treatment received in the VMDN-003 study.

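### The PGIC form does not say which study's start is meant, while the SAP reads every answer as change from the VMDN-003 baseline, so some subjects may rate only the extension period

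*Protocol*

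**What the plan says.** The form in Protocol Appendix 4 has one item, "Since the start of the study, my overall status is", seven boxes, and space for initials and a date. It does not say which study is meant.

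SAP 8.4 fixes the reference point for the analysis: "The change will be assessed relative to the VMDN-003 baseline". It groups the seven boxes into three categories and compares the arms with a stratified Cochran-Mantel-Haenszel row mean scores test.

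Protocol 4.4 describes the measure differently again: "The patient's global impression of change after treatment will be measured", and "This questionnaire measures a patient's perception of how treatment has affected their level of activity, symptoms, emotions, and overall quality of life". It gives no date and names no study.

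On entry to the extension, Protocol 3.2 says that eligible subjects "will be invited to provide informed consent and enroll in this extension study". Protocol 3.4.3 sets the timing: "Study subjects may sign the informed consent form for the extension study after completing Day 270 assessments for study VMDN-003", or at a later return visit "no later than 14 days prior to their scheduled Day 365 visit to sign the informed consent form".

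PGIC at Day 365 is one of three secondary efficacy endpoints (Protocol 5.6.2). It is collected once in this study (Protocol Appendix 1, Schedule of Evaluations).

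**The concern.** A subject who fills in this form has been in two studies and signed a consent for each. The form refers to one start without saying which. The protocol's own usage adds to the ambiguity: sections 3.3.1, 3.3.2, 3.4.4 and 3.5.1 use the plain word 'study' for the extension and generally name the parent trial as VMDN-003. A subject who has recently signed into a new study could reasonably count from there.

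An answer counted from extension consent leaves out the injections and about nine months of follow-up, so it is not the quantity that SAP 8.4 analyses. The form does not record which anchor the subject used. The coordinator check in Protocol 4.4 covers missing or ambiguous answers, and a clear tick made for the wrong period is neither. Unlike a diary score, a global rating cannot be recomputed against a stored baseline value.

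**Working it through.** **The three texts side by side**

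| Place | Reference point | Seen by the subject when answering? |
|---|---|---|
| Protocol Appendix 4 (form) | Start of an unnamed study | Yes |
| Protocol 4.4 | After treatment, no date | No |
| SAP 8.4 | VMDN-003 baseline | No |

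Protocol 4.4 and SAP 8.4 are compatible, since all injections were given in VMDN-003. The form can be read either way. The gap is an undefined term on the form, not a contradiction between the documents.

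**Length of the two possible recall periods**

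Inputs: visit at Day 365 ± 14 from VMDN-003 Day 0 (Protocol 3.2); consent from completion of Day 270 until 14 days before the scheduled visit (3.4.3); consent within 90 days of Day 270, so up to about Day 360 (3.3.1, criterion 3). The Day 270 visit is taken to fall on Day 270.

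- Counted from VMDN-003 Day 0: the visit day itself.
- Counted from consent at Day 270: visit day − 270.
- Counted from the latest permitted consent: visit day − min(visit day − 14, 360).

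| Visit day | From VMDN-003 Day 0 | From consent at Day 270 | From latest consent |
|---|---|---|---|
| 351 | 351 | 351 − 270 = 81 | 351 − 337 = 14 |
| 365 | 365 | 365 − 270 = 95 | 365 − 351 = 14 |
| 379 | 379 | 379 − 270 = 109 | 379 − 360 = 19 |

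The last scheduled injection was on Day 104, so Day 270 comes 270 − 104 = 166 days after it.

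**Effect on the arm difference**

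The plan gives no PGIC rate, effect size or sample size, so there is no figure to reproduce. SAP 3.2 states that the study was not designed for power. Let q be the share of subjects who rate from extension consent, equal in both arms and unrelated to how much a subject benefited. Let d be the arm difference on the VMDN-003 anchor and e the arm difference over the extension period. Then

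observed difference = (1 − q) × d + q × e.

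If e = 0, this is (1 − q) × d. The same factor applies to a difference in proportions and to a difference in mean category scores.

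Illustration with assumed rates of much or very much improved: 50% against 30% on the VMDN-003 anchor (d = 20 points), and 20% in both arms on the extension anchor (e = 0).

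| q (assumed) | One arm | Other arm | Difference |
|---|---|---|---|
| 0 | 50% | 30% | 20 points |
| 0.10 | 0.9 × 50 + 0.1 × 20 = 47% | 0.9 × 30 + 0.1 × 20 = 29% | 18 points |
| 0.25 | 0.75 × 50 + 0.25 × 20 = 42.5% | 0.75 × 30 + 0.25 × 20 = 27.5% | 15 points |
| 0.50 | 0.5 × 50 + 0.5 × 20 = 35% | 0.5 × 30 + 0.5 × 20 = 25% | 10 points |

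No row is more likely than another on the evidence of the documents.

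**The case against.** Much in the documents favours the VMDN-003 reading. Protocol 4.4 ties the PGIC to treatment, and the extension gives none. Subjects keep their VMDN-003 identifier (3.4.2), the visit is counted from VMDN-003 Day 0 (3.2), and the title calls this an extension of that trial. The sample consent form was removed from the text under review and the study worksheets are not included, so an explanation given there cannot be ruled out.

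This stands, and it limits the point. A reader might infer that some answers will refer to the wrong period; the documents contain nothing on how subjects understand the line, so only 'may' is supported. A reader might also put a size on the loss, for instance an arm difference cut to between 80% and 50% of its true value. That only restates a chosen q of 20% to 50%. It also needs no arm difference after Day 270, which the Day 270 to Day 365 pain endpoint is there to examine. Nor is it certain that extension-period answers would cluster at no change, because status could improve or worsen after Day 270.

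None of this defines the term on the form. The identifier, the visit schedule and Protocol 4.4 are not in front of the subject when the box is ticked, and even if the consent form explains the anchor, it may have been signed up to about three months earlier.

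**Conclusion.** The point holds as an ambiguity with a risk of misanchored answers, not as a contradiction or a demonstrated error. The form leaves its reference point open, the SAP assumes one reading for everyone, and the data will not show which reading a subject used. A subject on the other reading would rate 81 to 109 days (consent at Day 270), or as few as 14 days, instead of about 365.

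The effect on the comparison cannot be sized from the documents. The factor 1 − q rests on three assumptions: an unknown q of zero or more, the same q in both arms, and no arm difference over the extension period. Under these the result is attenuation, not a spurious benefit, and nothing in the documents suggests that misreading would differ by arm.

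Severity is minor. PGIC is a secondary endpoint, the primary endpoint is adverse events, the study is unpowered, and Protocol 5.6.3 calls its analyses descriptive only.

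**What to change.** Keep the scale wording. Add one instruction line to the form, such as: *Start of the study means before your first injection in VMDN-003 (date: ____)*, with the coordinator entering the Day 0 date before the subject answers. State the same anchor in Protocol 4.4 so that it matches SAP 8.4, which needs no change on this point.

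The cost is one line on a form and a minor protocol edit. The small downside is that the form is no longer identical to one without the instruction. If forms have already been completed, leave the data as they are and report the undefined anchor as a limitation of the PGIC result.

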This statistical analysis plan (SAP) describes the planned analysis and reporting for Helixmith Co., Ltd. protocol number VMDN-003b (long-term, prospective, non-interventional, safety extension of a phase III, double-blind, randomized, placebo-controlled, multicenter study to assess the safety and efficacy of VM202 in subjects with painful diabetic neuropathy), version C, dated 30-Jul-2019. Reference materials for this statistical plan include the protocol and the accompanying sample data collection documents. Operational aspects related to collection and timing of planned clinical assessments are not repeated in this SAP unless relevant to the planned analysis.

The structure and content of this SAP provides sufficient detail to meet the requirements identified by the Food and Drug Administration (FDA), European Medicines Agency (EMA), and International Conference on Harmonization (ICH) of Technical Requirements for Registration of Pharmaceuticals for Human Use: Guidance on Statistical Principles in Clinical Trials. All work planned and reported for this SAP will follow internationally accepted guidelines, published by the American Statistical Association and the Royal Statistical Society, for statistical practice.

The planned analyses identified in this SAP may be included in clinical study reports (CSRs), regulatory submissions, or future manuscripts. Also, post-hoc exploratory analyses not necessarily identified in this SAP may be performed to further examine study data. Any post-hoc or unplanned, exploratory analysis performed will be clearly identified as such in the final CSR.

The statistical plan described hereafter is an *a priori* plan. It will be submitted to file prior to any unblinded inferential or descriptive analysis of data pertaining to Helixmith Co., Ltd.'s study VMDN-003b.

2. Study Objectives and Endpoints

